## Revision History

SAP version	Revision Date (DD/MM/YYYY)	List of Changes
2.0	Mar 07, 2017	
 
• Added Section 5.4 Health Economic Data
 
• Added Bayesian adaptive design to select the final sample size of the trial in Section 8.2
 
• Added Appendix A: Simulation results for the operating characteristics of the trial
 
• Added Appendix B: Simulation R Code
 

3.0	May 01, 2017	Modified Section 3.0 to add an independent statistician from outside of the sponsor’s biostatistics group to conduct the interim analysis
4.0	April 30, 2018	
 
1. Removed Bayesian adaptive design from the following section: 
 
• Section 3.0 Study design: “The sample size of the trial will be determined by Bayesian adaptive techniques. ...The time of this analysis will not be revealed to study investigators, and the predicted probability of study success or summary results which are calculated at the time of the interim analysis will not be disseminated by the independent statistician performing the interim analysis until the time of the final database lock for the CSR.”
 
• Section 8.2 Sample Size: revised to remove the Bayesian adaptive design in sample size decision.
 
• Appendix A & B: removed the whole section regarding the simulation results for the operating characteristics of the trial and the simulation R code.
 
 
 
2. Added the following section per the template of SAP SOP: 
 
• Treatment Assignment
 
• Randomization and Blinding Procedures
 
 
 

		

• Interval Windows

• Level of Significance

• Sample Size Justification: combined sections of sample size and performance goal into this section

--	--	---

## **1 Introduction**

The purpose of this study is to demonstrate the safety and effectiveness of the THERMOCOOL® SMARTTOUCH™ SF catheter in the treatment of drug refractory symptomatic persistent atrial fibrillation (PsAF) following standard electrophysiology mapping and RF ablation procedures.

This statistical analysis plan contains a detailed description of the statistical analyses and data presentations that will be included in the clinical study report. The statistical methods and analyses described here are based on those presented in Section 7.0 of the study protocol (Version 6.0, 10 April 2018).

## **2 Study Design**

The PRECEPT study is a prospective, multicenter, non-randomized clinical evaluation utilizing the THERMOCOOL® SMARTTOUCH™ SF catheters compared to predetermined performance goals for safety and effectiveness. Up to 367 subjects will be enrolled at up to 35 sites (approximately 30 US and up to 5 OUS).

All patients considered for a RF ablation procedure for drug refractory recurrent symptomatic PsAF should be screened. Subjects who sign the informed consent form will be enrolled in the PRECEPT study and complete the screening assessments. Eligible subjects will undergo pre-procedure assessments within 30 days prior to the initial ablation procedure, which include transthoracic echocardiogram (TTE), imaging for detection of LA thrombus, pregnancy test, electrocardiogram (ECG), baseline 24 hour Holter monitor, baseline medical history, NIH Stroke Scale (NIHSS) assessment, arrhythmias history (including findings from TTM, ECG, Holter monitor, etc.), concomitant cardiac medications (including anticoagulation regime and failed AADs), and baseline quality of life assessment (including AFEQT and Symptoms Severity and Frequency Checklist).

After the index ablation procedure, subjects will enter a 3-Month Medication Adjustment Period followed by a 3-Month Therapy Consolidation Period (Day 0-180). Medication adjustment and repeat ablation may be performed during these periods as necessary.

After the 3-Month Therapy Consolidation Period, the subject will enter the Evaluation Period (Day 181-450). During evaluation period, subjects will undergo follow up visits at predefined intervals to receive study assessments. Subjects complete the PRECEPT study after the 15-month follow up visit.

### **3 Treatment Assignment**

This is a single-arm study and all enrolled patients for the study will be assigned to the study treatment.

### **4 Randomization and Blinding Procedures**

This study is a non-randomized single-arm study. No randomization or blinding procedure will be performed.

### **5 Interval Windows**

Please refer to the table 5-1 in the section 5.12 of protocol v 6.0.

### **6 Study Endpoints**

#### **6.1 Primary Endpoints and Associated Hypotheses**

##### **6.1.1 Primary Effectiveness Endpoint**

The primary effectiveness endpoint is defined as achieving effectiveness success after undergoing an RF ablation procedure using the THERMOCOOL® SMARTTOUCH™ SF catheter.

The null and alternative hypotheses are:

*Hypothesis:*  $H_0: P_E \leq 0.40$

$H_a: P_E > 0.40$

where  $P_E$  is the proportion of subjects who meet the effectiveness success criteria at 15 months follow-up

A subject has reached the effectiveness success if the subject is free from documented atrial tachyarrhythmia, including atrial fibrillation, atrial flutter and atrial tachycardia (AF/AFL/AT), recurrence (episodes  $\geq 30$  secs on Holter recordings/TTM or continuously recorded on the standard 12-leads ECG) during the evaluation period (Day 181-450) and free from the following failure modes:

- Acute procedural failure, including
  - Failure to confirm entrance block in all pulmonary veins post-procedure,
  - Use of a non-study catheter to treat the study arrhythmia for initial ablation,

- Non-study catheter failure while treating the study arrhythmia for repeat ablation procedure during the 3-Month Medication Adjustment or 3-Month Therapy Consolidation Period
- Repeat ablation failure, including
  - >2 repeat ablation procedures during the 3-Month Medication Adjustment Period / 3-Month Therapy Consolidation Period (Day 0-180) after the index procedure,
  - Any repeat ablation procedure during the evaluation period.
- AAD failure: Taking a new AAD or a previously failed AAD at a greater than the highest ineffective historical dose for AF during the evaluation period.
- Surgical failure: Undergoing surgical AF ablation or AF surgery any time after the index procedure.

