4.0 STUDY ENDPOINTS

4.1 Primary Endpoints

4.1.1 Primary Effectiveness Endpoint

The primary effectiveness endpoint is defined as the freedom from documented atrial fibrillation, atrial flutter and atrial tachycardia (AF/AFL/AT) (hereinafter collectively referred to as "atrial tachyarrhythmias") recurrence (episodes ≥ 30 secs on Holter recordings/TTM or continuously recorded on the standard 12-leads ECG) during the evaluation period (Day 181-450) and freedom from the following failure modes:

- Acute procedural failure, including:
 - Failure to confirm entrance block in all pulmonary veins post-procedure,
 - Use of a non-study catheter to treat the study arrhythmia for the initial ablation procedure.

Device deficiency of a non-investigational device leading to the use of a non-study catheter (i.e., Stockert 70, SMARTABLATE™ RF Generator and COOLFLOW® Pump, SMARTABLATE™ Irrigation Pump), during the AF procedure will not be considered an acute failure.

- Non-study catheter failure:
 - Use of a non-study catheter to treat the study arrhythmia for repeat ablation procedure during the 3-Month Medication Adjustment or 3-Month Therapy Consolidation Periods.
- Repeat ablation failure, including:
 - > 2 repeat ablation procedures during the 3-Month Medication Adjustment Period / 3-Month Therapy Consolidation Period (Day 0-180) after the index procedure.
 - Any repeat ablation procedure during the Evaluation Period.

Refer to section 5.18 for details.

- AAD failure: Taking a new AAD or a previously failed AAD at a greater than the highest ineffective historical dose for AF during the evaluation period (refer to section 5.14 for details).
- Surgical failure: Undergoing surgical AF ablation or AF surgery any time after the index procedure.

In summary, effectiveness success is defined as freedom from atrial tachyarrhythmia during the Evaluation Period, off or on a previously failed AAD, and not exceeding 2 repeat ablation procedures for an atrial tachyarrhythmia during the 3-Month Medication Adjustment and 3-Month Therapy Consolidation Periods.

This study is designed to compare the primary effectiveness of the investigational device to a pre-determined performance goal of 40%, which is indicated as the minimum acceptable success rate at 12 months for a persistent AF population in the 2012 HRS

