5.18.1 Repeat Ablation and Primary Effectiveness Classification

- Repeat Ablations in Day 0-180:
 - **Medication Adjustment Period** (Day 0-90): is intended to allow for the patient to receive medication and to allow remodeling to occur. Repeat ablations are discouraged, but subjects requiring a repeat ablation during this period will not be classified as primary effectiveness failures.
 - **Therapy Consolidation Period** (Day 91-180): During this interval, subjects undergoing up to 2 repeat ablations will not be classified as primary effectiveness failures. Circumstances associated with the repeat ablation(s) must be documented in the medical records and recorded in the eCRFs.

During the Medication Adjustment and Therapy Consolidation Periods, a subject may undergo up to 2 repeat ablations. More than 2 repeat ablations during these periods will result in classification as a primary effectiveness failure. Using non-study catheters in repeat ablation procedures during these periods will also be classified as a primary effectiveness failure.

- Repeat Ablation in Day 181-450:
 - During the **Evaluation Period** (Day 181-450), all subjects who have a repeat ablation will be classified as a primary effectiveness failure.
 - The study catheter may NOT be used to perform repeat ablations during the Evaluation Period (Day 181-450)

Table 5-5 illustrates the corresponding primary effectiveness classifications based on the number of repeat ablations in the 3-Month Medication Adjustment Period and 3-Month Therapy Consolidation Period and Evaluation Periods.

Table 5-5 Repeat Ablations and Impact on Primary Effectiveness Classification

Repeat Ablations		
Medication Adjustment Period: (Day 0-90)	Therapy Consolidation Period: (Day 91-180)	Evaluation Period: (Day 181-450)

 ● ≤ 2 repeat ablations are allowed ● Using non-study catheter will be classified as a primary effectiveness failure 		If subject undergoes any repeat ablation; Subject will be classified as a primary effectiveness failure. Use of study catheter not allowed
Repeat Ablations are discouraged Subject will NOT be classified as a primary effectiveness failure.	Subject will NOT be classified as a primary effectiveness failure.	

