### **10.4 Primary Endpoints Analyses**

#### **10.4.1 Primary Effectiveness Endpoint**

The primary effectiveness endpoint is defined as achieving effectiveness success at 12 months after undergoing an RF ablation procedure using the THERMOCOOL® SMARTTOUCH™ SF catheter. The primary effectiveness rate will be compared to a pre-determined performance goal of 40%.

The primary effectiveness endpoint will be evaluated by constructing the two-sided 95% exact confidence interval for the effectiveness rate. If the lower bound of the exact confidence interval of the primary effectiveness endpoint rate is greater than the performance goal of 40%, the study will be considered to have demonstrated effectiveness of the device.

The per protocol population (PP) will be used as the primary analysis population for effectiveness. Subjects with missing effectiveness data during the 15-month follow-up period will be excluded from the primary analysis.

Analyses of the primary effectiveness endpoint will be repeated using the mITT population. Subjects with catheter inserted but no RF delivered due to investigational device deficiency in the mITT population will be categorized as effectiveness failures and included in the analysis. Subjects with no RF delivery due to other reasons (e.g. anatomical difficulty, complications) will be excluded from the mITT analysis and be included in the sensitivity analysis for missing data.

Sensitivity analyses for missing data will be performed using the PP and mITT populations to assess the impact of missingness on the primary effectiveness outcome and are outlined in section 10.4.3.

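### SAP 6.1.1 drops the protocol's exemption for generator or pump faults, and loses the word for use in its repeat-ablation failure mode, so the written primary endpoint rules differ

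*SAP*

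**What the plan says.** **Initial procedure.** Protocol 4.1.1 lists as an acute procedural failure "Use of a non-study catheter to treat the study arrhythmia for the initial ablation procedure". It then adds an exception: "Device deficiency of a non-investigational device leading to the use of a non-study catheter", with named RF generators and irrigation pumps as the devices meant, "during the AF procedure will not be considered an acute failure". SAP 6.1.1 keeps the failure mode, "Use of a non-study catheter to treat the study arrhythmia for initial ablation", without the exception.

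**Repeat procedures, Day 0-180.** Protocol 4.1.1 has a failure mode named for the non-study catheter, and the rule under that name is "Use of a non-study catheter to treat the study arrhythmia for repeat ablation procedure during the 3-Month Medication Adjustment or 3-Month Therapy Consolidation Periods". Protocol 5.18.1 says it again: "Using non-study catheters in repeat ablation procedures during these periods will also be classified as a primary effectiveness failure". Table 5-5 of the protocol agrees. SAP 6.1.1 has a single bullet instead: "Non-study catheter failure while treating the study arrhythmia for repeat ablation procedure during the 3-Month Medication Adjustment or 3-Month Therapy Consolidation Period".

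**Other device-deficiency text in the SAP.** The only such rule is in SAP 10.4.1: "Subjects with catheter inserted but no RF delivered due to investigational device deficiency in the mITT population will be categorized as effectiveness failures". It concerns the investigational device, subjects with no RF, and the mITT analysis.

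**The concern.** SAP 6.1.1 is the list from which success and failure will be programmed. It reads as complete and has no cross-reference to protocol 4.1.1. SAP section 1 ties the methods to protocol Section 7.0, and SAP 9.1 points to protocol 4.1 only for the justification of the performance goal. Neither brings the exemption back in.

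Two kinds of subject could then be scored differently by the two documents, in opposite directions. One is switched to another catheter at the index procedure because of a generator or pump fault. The other has a repeat ablation with a non-study catheter that worked. The trial has a single arm, is open-label and is judged against a fixed 40% goal, so the definition of failure should be settled before the outcome data are analysed.

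**Working it through.** **1. The texts side by side**

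| Situation | Protocol | SAP as written |
|---|---|---|
| Index procedure, non-study catheter used, no device fault | Failure (4.1.1) | Failure (6.1.1) |
| Index procedure, non-study catheter used because of a generator or pump deficiency | Not an acute failure (4.1.1) | Failure (6.1.1) |
| Repeat in Day 0-180, non-study catheter used and it works | Failure (4.1.1, 5.18.1, Table 5-5) | Not a failure if read literally; failure if read as the protocol intends |
| Repeat in Day 0-180, non-study catheter used because of a generator or pump deficiency | Failure by the use rule; whether the exemption reaches this case is not stated | Depends on the reading of the bullet |

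**2. Who is affected by the missing exemption**

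The primary analysis is in the per-protocol set, which requires RF ablation and treatment with the study catheters (SAP 8). A subject switched before any study-catheter RF appears to fall outside it. In the mITT analysis, a subject with no RF for reasons other than investigational device deficiency is excluded and goes to the missing-data sensitivity analysis (SAP 10.4.1). What remains is mainly the subject who received some study-catheter RF, was then switched because of a generator or pump fault, and is otherwise a success.

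**3. The plan's decision rule**

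Inputs from SAP 9.1 and 10.4.1: goal 0.40, expected rate 0.50, n = 330, and success if the exact two-sided 95% lower bound exceeds 0.40.

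- 151/330 (45.8%) has an exact lower bound of 40.29% and passes. 150/330 has 39.99% and does not.
- P(X ≥ 151 | n = 330, p = 0.40) = 1.9%.
- P(X ≥ 151 | n = 330, p = 0.50) = 94.5%, so the plan's claim of at least 90% power holds.
- One rescored subject moves the rate by 1/330 = 0.30 points.

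**4. Missing exemption (downward)**

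Let f be the share of protocol-defined successes that the SAP scores as failures. No count is given, so f is assumed. The SAP rate is 0.50 × (1 − f), and the expected number of rescored subjects is 330 × 0.50 × f.

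| f | Rescored subjects | SAP rate | Power |
|---|---|---|---|
| 0 | 0 | 0.500 | 94.5% |
| 1% | 1.65 | 0.495 | 92.2% |
| 2% | 3.3 | 0.490 | 89.1% |
| 3% | 4.95 | 0.485 | 85.4% |

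The base of the percentage matters. If f were a share of all subjects, all of them otherwise successes, the rate would be 0.50 − f. Then 1%, 2% and 3% would give power of 89.1%, 80.8% and 69.4%.

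**5. Literal repeat-ablation wording (upward)**

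Let k be the extra expected successes per 330 (assumed) when the protocol-defined rate is exactly 40%. The SAP rate is 0.40 + k/330.

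| k | SAP rate | P(X ≥ 151) |
|---|---|---|
| 0 | 0.4000 | 1.9% |
| 1 | 0.4030 | 2.5% |
| 3 | 0.4091 | 4.2% |
| 5 | 0.4152 | 6.6% |

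**The case against.** The best defence concerns the repeat-ablation bullet. In protocol 4.1.1 the opening words of that bullet are the name of a failure mode, and the SAP seems to have run the name into the text below it. The other modes are named the same way. AAD failure means taking a drug, surgical failure means undergoing surgery, and repeat ablation failure means having too many or late repeats. On that pattern the SAP bullet means failure through a non-study catheter, not malfunction of one. A rule that failed the subject only if the other catheter broke would have no rationale in either document. This stands as to intent. It does not repair the wording: the word for use is gone from this bullet while the initial-ablation bullet keeps it, and a programmer could take the contrast as deliberate.

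On the exemption, it can be said that few subjects are touched, for the reasons in step 2 of the working, and that scoring them as failures cannot create a false pass. Both stand, and both limit the size. They do not remove the conflict, because the same subject still has two different outcomes in two current documents.

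A reader might infer two stronger claims. The first is that the SAP credits the study catheter with another device's repeat procedure and so inflates the false-pass risk, for example to 9.3% if the rate rose from 40% to 42%. That needs the less natural reading. It also needs 0.02 × 330 = 6.6 subjects with non-study repeats, all otherwise successes, and the documents give no such figure. If half of them succeeded (also assumed), the rate would be 41% and the pass probability 4.5%. The second is that every subject switched for a generator or pump fault fails under the SAP. The per-protocol definition and the mITT rule do not support that.

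**Conclusion.** The SAP is wrong as written, with minor severity. The firm part is the omitted exemption, which makes the SAP stricter than the protocol for a narrow group and costs power rather than protection. At f = 2% of protocol successes, power is just below the planned 90%. The weaker part is the repeat-ablation bullet, a drafting slip whose intent is probably the protocol's. It would raise the false-pass probability only if the literal text were programmed. All these sizes rest on assumed counts, at 330 evaluable subjects. The two errors act in opposite directions, but nothing makes them cancel. The effect is likely to be small unless several subjects are involved. Since 150 and 151 successes fall on different sides of the goal, even one subject could matter in a close result.

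**What to change.** In SAP 6.1.1:

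1. Under acute procedural failure, add the protocol 4.1.1 sentence that exempts non-study catheter use caused by deficiency of a non-investigational device.
2. Replace the repeat-ablation bullet with the protocol sentence, "Use of a non-study catheter to treat the study arrhythmia for repeat ablation procedure during the 3-Month Medication Adjustment or 3-Month Therapy Consolidation Periods".
3. Reconcile the two documents on whether the exemption also applies to repeat procedures. Protocol 4.1.1 places it under acute failure only, and protocol 5.18.1 states the repeat rule without it.

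The cost is two copied sentences and one clarification, made before the endpoint is programmed. The sample size (330 evaluable, 367 enrolled), the significance level and the performance goal do not change.

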### 6.1.2 Primary Safety Endpoint

The primary safety endpoint is the incidence of any primary adverse event (PAE) occurring within 7 days of the AF ablation procedure (including the initial and repeat procedures) using the study catheter per protocol.

The null and alternative hypotheses are:

*Hypothesis:*  $H_0: P_S \geq 0.16$

$H_a: P_S < 0.16$

where  $P_S$  is the proportion of subjects with the early onset (within seven days of the initial and repeat ablation procedure for AF) primary AE

PAEs include the following conditions:

 
• Death
 
• Atrio-esophageal fistula*
 
• Cardiac Tamponade**/Perforation†
 
• Myocardial infarction (MI)
 
• Stroke / Cerebrovascular accident (CVA)†,††
 
• Thromboembolism
 
• Transient Ischemic Attack
 
	
 
• Diaphragmatic paralysis
 
• Pneumothorax
 
• Heart block
 
• PV stenosis*
 
• Pulmonary edema (Respiratory Insufficiency)
 
• Pericarditis
 
• Major vascular access complication / bleeding
 

---	--

- \* Pulmonary vein (PV) stenosis and atrio-esophageal fistula that occurs greater than one week (7 days) post-procedure shall be deemed Primary AEs.
- \*\* Hemodynamic compromise or instability is defined as Systolic BP < 80 mm Hg.
- + Cardiac Tamponade/Perforation occurring within 30 days of the AF ablation process will be considered Primary AEs
- † Subjects with non-focal global encephalopathy will not be reported as a stroke without unequivocal evidence based upon neuroimaging studies.
- †† Modified Rankin score assessments should be made by qualified individuals according to a certification process. If there is discordance between the 30 and 90 day Modified Rankin scores, a final determination of major versus minor stroke will be adjudicated by the neurology members of the Global Safety Monitoring Committee (GSMC).

## 6.2 Secondary Endpoints

### 6.2.1 Secondary Effectiveness Endpoints

- Acute Procedural Success: Acute procedural success is defined as confirmation of entrance block in all PVs.
- 15-Month Single Procedure Success
  - The 15-month single procedure success is defined as freedom from documented AF/AFL/AT recurrence (episodes  $\geq$  30 secs) during the Evaluation Period after one single ablation procedure. Any repeat ablation procedure after the initial ablation will be deemed effectiveness failures.
  - The 15-month single procedure success is defined as freedom from documented symptomatic AF/AFL/AT recurrence (episodes  $\geq$  30 secs) during the Evaluation Period after one single ablation procedure. Any repeat ablation procedure after the initial ablation will be deemed effectiveness failures.

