### 8 Analysis Sets

For the analysis of study endpoints, the analysis populations are defined as the following:

- **Modified Intent-To-Treat (mITT) Population:** the mITT population will consist of all enrolled subjects who meet all eligibility criteria AND in whom
  - (1) RF energy was delivered with study catheter OR
  - (2) Study catheter was inserted but no RF energy was delivered
- **Safety Population (SP):** The safety population will consist of all enrolled subjects who have undergone insertion of the study catheter. Safety endpoints will be analyzed based on the Safety Population.
- **Per Protocol (PP) Population:** The PP population will include subjects who satisfy the following criteria:
  - are enrolled and meet all eligibility criteria
  - have undergone RF ablation
  - are treated with the study catheters, and have been treated for the study-related arrhythmia

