#### **10.5.1 Secondary Effectiveness Endpoints**

##### **10.5.1.1 Acute Procedural Success**

The number and percentage of subjects with acute procedural success and the corresponding 95% exact binomial confidence interval will be presented. Analysis will be conducted based on PP population.

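### Acute procedural success has no study-catheter condition and is analysed only in PP, so this descriptive rate can overstate the study catheter if non-study catheter use or device-deficiency non-treatments occur

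*SAP*

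**What the plan says.** The secondary endpoint is defined in the same terms in SAP 6.2.1 and protocol 4.2.1: "Acute procedural success is defined as confirmation of entrance block in all PVs". SAP 10.5.1.1 names the analysis set: "Analysis will be conducted based on PP population".

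The primary endpoint lists acute procedural failure among its failure modes, in two forms (SAP 6.1.1; protocol 4.1.1 has equivalent wording):
- "Failure to confirm entrance block in all pulmonary veins post-procedure"
- "Use of a non-study catheter to treat the study arrhythmia for initial ablation"

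Protocol 4.1.1 adds one exemption, which SAP 6.1.1 does not repeat. "Device deficiency of a non-investigational device leading to the use of a non-study catheter", for example of the generator or irrigation pump, is not an acute failure.

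SAP section 8 limits PP to eligible subjects who "have undergone RF ablation" and who "are treated with the study catheters, and have been treated for the study-related arrhythmia". It does not say whether treatment must be with the study catheters only.

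For the mITT repeat of the primary analysis, SAP 10.4.1 says: "Subjects with catheter inserted but no RF delivered due to investigational device deficiency in the mITT population will be categorized as effectiveness failures". Subjects with no RF for other reasons are left out of that analysis and taken up in the missing-data sensitivity analyses.

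**The concern.** The two endpoints use the same label, acute procedural, with different rules. The primary endpoint asks whether the veins were isolated and whether the study catheter did the work. The secondary endpoint asks only the first question. A subject whose isolation was completed with another catheter, outside the exemption, is an acute failure under one rule and meets the definition of acute success under the other.

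The choice of analysis set adds a second gap. A subject in whom the study catheter was inserted but could deliver no RF because it was deficient is informative about acute device performance. That subject is outside PP and so never enters this rate.

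The trial's stated purpose is to demonstrate the safety and effectiveness of this catheter. The acute success rate will be read as a measure of what the catheter achieved, and as defined it need not be one.

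**Working it through.** **No figure to reproduce.** The documents state no rate, goal, sample size or power for acute procedural success. The check is a comparison of the rules, followed by an illustration on assumed counts.

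**Step 1: how each rule treats the same subject.**

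| Subject | Primary endpoint | Acute procedural success |
|---|---|---|
| All veins blocked, study catheter only | Not an acute failure | Success |
| All veins blocked, non-study catheter used at the initial ablation, no exemption | Acute failure | Success if PP is not exclusive; not in the denominator if it is |
| Same, after a non-investigational device deficiency | Not an acute failure (protocol 4.1.1) | Success if PP is not exclusive; not in the denominator if it is |
| Inserted, no RF, investigational device deficiency | Outside PP; failure in the mITT repeat | Not in the denominator |

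In the second and fourth rows, the subject counts against the device in a primary-endpoint analysis and does not count against it in acute procedural success.

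**Step 2: direction.** Let N be subjects with RF ablation who are in PP on the non-exclusive reading, B those with block in all veins, k those within B who had non-exempt non-study catheter use, and e the inserted-but-no-RF device-deficiency subjects.

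- As written, PP not exclusive: B/N
- As written, PP exclusive: (B − k)/(N − k)
- Study catheter only, same N: (B − k)/N
- Study catheter only, adding the no-RF device-deficiency subjects: (B − k)/(N + e)

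Neither as-written rate is ever below the study-catheter rate. All four are equal when k = 0 and e = 0. The PP-exclusive reading does not remove the effect. With B = N, it gives (N − k)/(N − k) = 100%, the same as the non-exclusive reading.

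**Step 3: size, on assumed counts.** N = 330 is the evaluable number in SAP 9.1, used only for scale. B = 330, k and e are assumptions.

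| k | e | As written | Study catheter only, PP | Study catheter only, mITT |
|---|---|---|---|---|
| 0 | 0 | 100% | 330/330 = 100% | 330/330 = 100% |
| 0 | 7 | 100% | 330/330 = 100% | 330/337 = 97.9% |
| 3 | 0 | 100% | 327/330 = 99.1% | 327/330 = 99.1% |
| 7 | 0 | 100% | 323/330 = 97.9% | 323/330 = 97.9% |
| 16 | 7 | 100% | 314/330 = 95.2% | 314/337 = 93.2% |
| 33 | 7 | 100% | 297/330 = 90.0% | 297/337 = 88.1% |

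The exact 95% interval is 97.4% to 99.8% for 327/330 and 95.7% to 99.1% for 323/330. For non-study catheter use the gap is k/N when B = N: 3/330 is 0.9 points and 7/330 is 2.1 points, so about 1 point per 1% of subjects. For no-RF subjects alone the gap is e/(N + e), or 7/337 = 2.1 points. The last row is an outer bound; nothing in the documents suggests counts that high.

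**The case against.** The strongest reply is that acute procedural success is a technical endpoint in its own right. Protocol 5.9 uses acute success for isolation of all pulmonary veins, and neither document calls the secondary endpoint the complement of the failure mode. Both rules can be applied to the same subject without either breaking down. That stands. A reader might infer that the plan flatly contradicts itself, but what the documents show is one label with two rules and an open question about PP.

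It can also be said that crediting any catheter is read into silence, because PP requires treatment with the study catheters. The ambiguity is real. However, an exclusive PP set removes non-study catheter users instead of counting them as failures, which also favours the device. It would also leave the initial-ablation catheter failure mode with nothing to count in the primary PP analysis.

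The plan does give related information. Protocol 4.3 and SAP 6.3 and 10.6.3 list the percentage of veins isolated with the study device, by vein, and the devices used per ablation. SAP 10.2 summarises subjects with insertion but no RF as a disposition category. These cases are therefore not hidden, but none of these outputs is a per-subject success rate for the study catheter.

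Finally, PP is the primary effectiveness population throughout, so its use here is consistent with the rest of the plan, not selective. That is fair. An mITT row adds information; its absence is not an error in itself.

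**Conclusion.** The point holds in conditional form. The definition carries no study-catheter condition, and the analysis set leaves out device-deficiency non-treatments. The reported rate can overstate the study catheter's acute performance if either kind of case occurs; if neither occurs, nothing changes. This direction holds on either reading of PP.

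The size is unknown. On the assumption that every other subject has block, each 1% of subjects affected costs about 1 point.

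Two stronger readings are not supported. A reader might infer that the rate is in fact inflated, but the documents give no count of non-study catheter use or of device-deficiency non-treatments. A reader might also infer that the effectiveness claim is at risk. It is not: secondary endpoints are descriptive, with no hypothesis (protocol 7.7, SAP 10.5), and no performance goal is set for this one. The primary endpoint already counts non-exempt non-study catheter use as failure, and its mITT repeat counts the device-deficiency subjects as failures. The primary test and the sample size are unaffected. This is a minor point, worth correcting because it is cheap to correct.

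**What to change.** - In SAP 6.2.1 and protocol 4.2.1, define acute procedural success as entrance block in all pulmonary veins with the study catheter only, at the index procedure.
- Show subjects under the protocol 4.1.1 non-investigational-device exemption on a separate line, neither credited to the study catheter nor counted as failures. Simply carrying the exemption into the definition would still credit isolation by another catheter to the study catheter.
- In SAP 10.5.1.1, repeat the analysis in mITT, with no-RF subjects due to investigational device deficiency as failures, in line with SAP 10.4.1.
- Keep the any-catheter rate alongside, labelled as such.
- State in SAP section 8 whether PP means study catheter exclusively.

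The cost is a few lines of wording, one extra table and, if such cases occur, a slightly lower reported rate. The devices used per ablation are already to be recorded, so no new data collection is evident.
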